9.3. Safety Analysis

Safety assessments will be made on the safety analysis population.

9.3.1. Adverse Events

AEs that occurred on or after the first dose in the MT-1186-A03 will be summarized, which implies AE that occurred during MT-1186-A01 will not be summarized.

The following summaries will be provided:

- A Summary table of the overall incidence (number and percentage) and the number of events will be provided for TEAE, TEAE related to study drug, severe TEAEs, TESAEs, TEAEs leading to study treatment discontinuation and TEAEs leading to death.

The numbers and proportions of subjects will be calculated for the following:

- TEAEs by SOC and PT
- TEAEs by SOC, PT and severity
- Most Common ($\geq 5\%$ of patients) TEAEs by SOC and PT
- TEAEs related to study drug by SOC and PT
- TEAEs related to study drug by SOC, PT and severity
- TESAEs by SOC and PT
- TESAEs related to study drug by SOC and PT
- Severe TEAEs by SOC and PT
- Severe TEAEs related to study drug by SOC and PT
- TEAEs leading to study treatment discontinuation by SOC and PT
- TEAEs by SOC, PT and relationship to study drug
- TESAEs by SOC, PT and relationship to study drug
- TEAEs leading to death by SOC and PT

For these tables, SOC will be sorted by International Agreed Order; then within SOC, PT will be sorted by PT code.

The following summaries will be provided:

- A Summary table of the overall incidence (number and percentage) will be provided for Peripheral Neuropathy Standardized MedDRA query (SMQ) TEAEs

The numbers and proportions of subjects will be calculated for the following:

- TEAEs of Peripheral Neuropathy SMQ by SOC and PT
- Serious TEAEs of Peripheral Neuropathy SMQ by SOC and PT

TEAEs by Oral/PEG subgroup, SOC and PT

The numbers and proportions of subjects with TEAEs and event rate of TEAEs will be calculated by Oral/PEG subgroup, SOC and PT. The event rate of TEAEs will be calculated as the number of TEAEs divided by total exposure to investigational product by Oral/PEG dosing and expressed as 100 person years. Any TEAE occurred after subject switched to PEG will be classified under the PEG subgroup.

The exposure (in days) under Oral in cycle switched to PEG will be calculated as difference: Oral days=PEG switch Date during MT-1186-A01 or MT-1186-A03 - Cycle first date. If Oral days is less than 0 then Oral days will be 0.

The oral days does not exceed actual exposure duration (days) in the cycle. The exposure under PEG will be calculated as difference:

PEG days= actual exposure duration - Oral days.

TEAEs by Cycle

The numbers and proportions of subjects with TEAEs will be calculated by Cycle of treatment and by SOC and PT. Cycles will be categorized into grouping of: Cycle 1-6, Cycle 7-12, Cycle 13-18 and Cycle 19-24.

For each of the summaries, multiple occurrences of the same event within a subject will be counted once in the summaries by SOC and PT; multiple occurrences of the same event within a subject will be counted once in the maximum severity category (severe > moderate > mild) and/or maximum study drug relationship category (reasonable possibility / no reasonable possibility). If severity or relationship is found to be missing the most severe occurrence will be imputed for that particular summary.

In the analysis of TEAEs by Cycle, reoccurrences of TEAE's per subject can be shown multiple times if occurred in different cycles categories. The TEAEs occurred at follow up period of subjects who completed the study will be categorized Cycle 19-24.

Subject's data listings will be provided for: TEAEs, TESAEs, TEAE leading to discontinuation of study drug and Death

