### **15.6 Recording and Reporting of Adverse Events**

All AEs, regardless of the relationship to IMP, occurring from the time written ICF will be obtained from a subject until the end of the safety Follow-up Period or the withdrawal of the subject from the study will be recorded.

NOTE: Elective hospitalization or procedure/surgery planned before subject enrollment for a preexisting medical condition does not constitute an AE unless the underlying disease or condition worsens after signing ICF.

All AEs will be recorded on an AE form in the eCRF. Reports should contain a description of the event, date of onset, date of resolution, severity, treatment required, relationship to IMP, action taken with the IMP, outcome and whether the event is classified as serious.

The Investigator will evaluate the severity of the AEs (as defined in Section 15.3) and will assess the causality between the AEs and the IMP (as defined in Section 15.4).

Pre-existing illnesses, which started prior to entry and are still ongoing at the start of the study, will not be considered AEs unless they worsen during the treatment period. Pre-existing conditions will be recorded as medical history.

If the Investigator becomes aware of any new safety information, or any safety information, which appears to be either study or IMP, related after the Final Follow-up period, then they must notify the Sponsor immediately.

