6. ANALYSIS POPULATIONS

6.1. Safety Analysis Population

The safety analysis population set is defined as all enrolled subjects to A03 who received at least 1 dose of oral edaravone.

6.2. Full Analysis Set:

The Full Analysis (FAS) is defined as all patients in the MT-1186-A01 SAF as defined in protocol MT-1186-A01. This analysis set will include patients who discontinued treatment during MT-1186-A01.

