7. STATISTICAL CONSIDERATIONS

7.1. Descriptive Statistics

All data from all subjects enrolled into the study will be included in patient data listings. The listings will be sorted by center and subject number (and by visit, if applicable).

Continuous data will be summarized descriptively using the number in the analysis population set (N), the number of observations (n), mean, standard deviation (SD), median, minimum and maximum. Categorical data will be summarized using frequency counts and percentages. The denominator for the percentages will be the total number of subjects in the treatment group and analysis population being presented, unless otherwise specified. For visit-specific data, the number of subjects with non-missing observations at the visit in question will be used as the denominator for percent calculations. Unknown, Not Done, Not Applicable and other classifications of missing data will not be considered.

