8.6. Cycle Definition

The cycles definition during MT-1186-A03 are specified in Table 6: Cycle definition. The date of the first dose of study drug in this study is defined as Day 1. The cycles have no time window definition. Differences between dosing cycles and analysis cycles may occur but will not be considered.

Table 6: Cycle definition

| Cycle | Day |
|--------------|------------------|
| Cycle 1 | Day 1 to 28 |
| Cycle 2 | Day 29 to 56 |
| Cycle 3 | Day 57 to 84 |
| Cycle 4 | Day 85 to 112 |
| Cycle 5 | Day 113 to 140 |
| Cycle 6 | Day 141 to 168 |
| Cycle 7 | Day 169 to 196 |
| Cycle 8 | Day 197 to 224 |
| Cycle 9 | Day 225 to 252 |
| Cycle 10 | Day 253 to 280 |
| Cycle 11 | Day 281 to 308 |
| Cycle 12 | Day 309 to 336 |
| Cycle 13 | Day 337 to 364 |
| Cycle 14 | Day 365 to 392 |
| Cycle 15 | Day 393 to 420 |
| Cycle 16 | Day 421 to 448 |
| Cycle 17 | Day 449 to 476 |
| Cycle 18 | Day 477 to 504 |
| Cycle 19 | Day 505 to 532 |
| Cycle 20 | Day 533 to 560 |
| Cycle 21 | Day 561 to 588 |
| Cycle 22 | Day 589 to 616 |
| Cycle 23 | Day 617 to 644 |
| Cycle 24 | Day 645 on later |

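### TEAE percentages by cycle block have no block-specific denominator, so under the SAP's default rule late-block percentages shrink with retention

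*SAP*

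**What the plan says.** SAP 9.3.1, under TEAEs by Cycle, states: "The numbers and proportions of subjects with TEAEs will be calculated by Cycle of treatment and by SOC and PT". The blocks are Cycles 1-6, 7-12, 13-18 and 19-24. A subject may be counted again in a later block, so each block is read as its own incidence. No denominator is given there. Protocol 17.3.5.3 does not list this table, so it supplies none either.

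The general rule is in SAP 7.1: "The denominator for the percentages will be the total number of subjects in the treatment group and analysis population being presented, unless otherwise specified". Its one exception is this: "For visit-specific data, the number of subjects with non-missing observations at the visit in question will be used as the denominator for percent calculations". For safety, SAP 9.3 says "Safety assessments will be made on the safety analysis population", and SAP 6.1 defines that set: "The safety analysis population set is defined as all enrolled subjects to A03 who received at least 1 dose of oral edaravone". Membership does not depend on remaining in the study.

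Protocol 15.6 limits the period of AE recording: events from consent "until the end of the safety Follow-up Period or the withdrawal of the subject from the study will be recorded".

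**The concern.** Taken together, these rules put every dosed subject under every block, including subjects whose AE recording ended long before the block began. The visit-specific exception does not help, because the SAP defines visits (Table 5) and cycles (Table 6) separately.

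Some loss is built into the design. Protocol 9.6 withdraws subjects for tracheostomy, permanent ventilation or worsening disease, and Protocol 10.1.2 lets treatment end when the drug becomes commercially available in a country.

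The primary objective is long-term safety, and this is the only planned TEAE incidence table by time block. A reader will use it to ask whether risk changes with time on drug. On the default base, that reading is mixed up with how many subjects are still being observed.

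**Working it through.** **Inputs from the documents**
- Blocks of 6 × 28 = 168 days, starting on Days 1, 169, 337 and 505 (SAP 9.3.1, Table 6). Check: 24 × 28 = 672 = 96 × 7.
- About 140 subjects (SAP 4.2).
- Default denominator: the whole safety population (SAP 7.1, 9.3, 6.1).

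**Not in the documents, so assumed:** retention, TEAE risk, constant hazards, and exit independent of TEAEs. The plan gives no figure of its own to reproduce.

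**Step 1: exits only between blocks.** Printed % = p × R, where p is the block risk among subjects still observed and R is the share still observed. For p = 20% and R = 100, 90, 70, 60, 50%, the table prints 20, 18, 14, 12, 10%. In counts, at R = 60%, 140 × 0.6 = 84 subjects are observed. If 17 have a TEAE, that is 17/84 = 20.2%, but the table shows 17/140 = 12.1%.

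In reverse, the risk that would still print as 20% is 20%/R: 28.6% at R = 70%, 33.3% at 60% and 40% at 50%. A real rise of that size would look flat.

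**Step 2: exits also inside blocks.** Take a TEAE hazard of 20% per 168 days and steady loss to 60% at Day 505, which is three block lengths after Day 1.
- TEAE hazard per block: λ = −ln(0.8) = 0.223.
- Exit hazard per block: μ = −ln(0.6)/3 = 0.170.
- Chance that a subject present at block start has a TEAE recorded in that block: λ/(λ+μ) × [1 − exp(−(λ+μ))] = 0.567 × 0.325 = 0.184.
- Share present at block start: 0.6 to the power 0, 1/3, 2/3, 1 = 1, 0.843, 0.711, 0.600.

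| Block | Present at start (of 140) | Default denominator | Block-start denominator |
|---|---|---|---|
| Cycle 1-6 | 140 | 18.4% | 18.4% |
| Cycle 7-12 | 118 | 15.6% | 18.4% |
| Cycle 13-18 | 100 | 13.1% | 18.4% |
| Cycle 19-24 | 84 | 11.1% | 18.4% |

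The risk is constant by construction. The default column falls only because subjects leave.

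**Step 3: other assumed values.** Use 30% per 168 days and exponential loss with a mean of 4 or 2 years. About 99 of 140 (71%) or 70 of 140 (50%) then reach Day 505.
- Mean 4 years: the default prints 28.4, 25.4, 22.6, 20.1%; the block-start base prints 28.4% throughout.
- Mean 2 years: the default prints 27.0, 21.5, 17.0, 13.5%; the block-start base prints 27.0% throughout.
- The first-event rate is 77.5 per 100 person-years at risk in every block under both loss patterns.

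The block-start percentage removes the false trend, but its level still depends on loss within the block (28.4 or 27.0%, not 30%). The person-time rate does not.

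**The case against.** The main points on the other side are these.

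- **A denominator is stated.** A reader might infer that the SAP gives none at all. It does: SAP 7.1 supplies one by default. This stands, and the point is only that the default does not suit a table by time block.
- **Table shells are not part of the documents.** They may set a per-block n. This stands as a condition on the conclusion.
- **The sizes are assumed.** This also stands. The documents support the direction if subjects leave, not an amount.
- **Timing can be recovered elsewhere.** The plan also gives counts, AE listings, disposition (SAP 9.1.1), exposure by cycle (SAP 9.1.6) and time to AE occurrence (SAP 8.4.3.1). These help a careful reader, but none is tied to these percentages. SAP 8.4.1.4 also does not say how cycles after exit are treated, so the n in the exposure table need not be the number at risk.
- **A block-start n is also a convention.** It counts a subject who leaves the next day as fully at risk. This stands, and is why the fix adds a rate.

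A reader might also infer that the follow-up rule misplaces events: "The TEAEs occurred at follow up period of subjects who completed the study will be categorized Cycle 19-24". The documents do not support calling that a defect. Week 96 is Day 96 × 7 + 1 = 673, already inside Cycle 24 ("Day 645 on later"), so the rule changes nothing for anyone followed that far. The Protocol synopsis and SAP 4.1 treat leaving before Week 96 as discontinuing, and Protocol 10.1.3 separates completers from early terminators. Protocol 10.1.2 and SAP 5.2 leave some doubt about exits at commercial availability, which justifies a clarification and no more.

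**Conclusion.** The concern holds as a minor one. As written, and unless a table shell says otherwise, the by-cycle percentages use the whole safety population in every block, so late-block values are roughly the at-risk percentage times retention. In the illustration, a constant risk prints as 18.4% falling to 11.1%, given 60% retention at Day 505, a 20% hazard per 168 days, constant hazards and independent exit. With full retention there is no distortion.

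A reader might infer that the study's safety results as a whole are understated. The documents do not support that. The overall TEAE, serious TEAE and death tables do not rely on block denominators, and SAP 7.2 plans no hypothesis test. The consequence is confined to how this one table reads.

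**What to change.** Add to SAP 9.3.1:

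> For TEAEs by Cycle, the denominator of each block is the number of safety-population subjects whose last A03 AE-collection date (last visit, ET or follow-up visit, or contact at which AEs were reviewed; survival-only calls excluded) is on or after the first day of the block (Day 1, 169, 337, 505; Table 6). This n is shown in the column header.

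The date has to be defined because the protocol does not use one cut-off. ET procedures may fall up to 7 days after discontinuation (Protocol 10.1.3), and calls after drug discontinuation check only for death, tracheostomy or ventilation (Protocol 13.2).

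Also present a TEAE rate per 100 person-years under AE collection in each block, to allow for exits during the block. Label it as a different basis from the Oral/PEG rate, which uses dosing-day exposure. Confirm that completing the study, in the follow-up rule, means followed to Week 96.

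Cost: slightly more programming and no new data. Late-block percentages may look less favourable than under the default.

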#### **10.1.2 End of Treatment**

The EOT visit will occur at Week 94, when the drug is commercially available in that country, or in the event the Sponsor discontinues the study.

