#### **10.1.3 Safety Follow-up Period/End of Study/Early Termination**

A safety follow-up period (e.g., Visit 9, Week 96 [ $\pm 7$  days]) will be conducted for subjects who complete the open-label treatment period, per the Schedule of Assessments (Table 1).

For subjects who terminate early from the study, assessments should be performed per the Schedule of Assessments (Table 1) within 7 days of study discontinuation.

Any unresolved AE or SAE will be followed up according to Section 15.8.

In the event that a subject elects not to return to the clinical site for the ET Visit, the Investigator must make every effort to contact the subject to review all AEs. In the event that a subject drops out of the study at any time, the reason for discontinuation must be fully documented in the source documents and the eCRF. The Investigator site personnel will document the AEs and any other assessments in the source documents and will make every effort to complete all required ET assessments.

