3. STUDY OBJECTIVE AND ENDPOINTS

3.1. Study Objectives

3.1.1. Primary Objective

To evaluate the long-term safety of oral edaravone at a dose of 105 mg administered once daily for 10 days out of a 14-day period, followed by a 14-day drug-free period for 96 weeks of treatment or until the drug is commercially available in that country.

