9. STATISTICAL METHODOLOGY

9.1. Study Subjects

9.1.1. Subject Disposition

Subject disposition will be listed and summarized using descriptive statistics. The percentages will be calculated based on the number of enrolled subjects, unless otherwise specified.

- The number of subjects enrolled in MT-1186-A01
- The number (%) of subjects in the full analysis set (% calculated from the number of enrolled subjects in MT-1186-A01)
- The number (%) of subjects who discontinued in MT-1186-A01 (% calculated from the number of enrolled subjects in MT-1186-A01)
- The number (%) of subjects completed MT-1186-A01 (% calculated from the number of enrolled subjects in MT-1186-A01)
- The number of subjects screened for MT-1186-A03
- The number (%) of subjects who failed screening, including the distribution of reasons for screen failure (% calculated from the number of screened subjects in MT-1186-A03)
- The number (%) of subjects enrolled in MT-1186-A03 (% calculated from the number of screened subjects in MT-1186-A03)
- The number (%) of subjects in the safety analysis population
- The number (%) of subjects who completed MT-1186-A03 (% calculated from the number of enrolled subjects in MT-1186-A03)
- The number (%) of subjects who discontinued in MT-1186-A03 including the distribution of reasons for discontinuation (% calculated from the number of enrolled subjects in MT-1186-A03)

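### If subjects who stop at commercial availability count as completers, SAP 9.3.1 may show their follow-up TEAEs as Cycle 19-24 events whatever their exposure

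*SAP*

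**What the plan says.** The objective in SAP 3.1.1 allows two durations: "for 96 weeks of treatment or until the drug is commercially available in that country". Protocol 10.1.2 makes availability an end-of-treatment trigger in its own right: "The EOT visit will occur at Week 94, when the drug is commercially available in that country". A third trigger is the sponsor stopping the study. Protocol 10.1.3 says a safety follow-up "will be conducted for subjects who complete the open-label treatment period", gives Visit 9 at Week 96 as its example, and states no minimum duration of treatment.

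For the by-cycle table, SAP 9.3.1 sets four blocks: "Cycles will be categorized into grouping of: Cycle 1-6, Cycle 7-12, Cycle 13-18 and Cycle 19-24". It then adds, with no condition on time treated: "The TEAEs occurred at follow up period of subjects who completed the study will be categorized Cycle 19-24". SAP 8.6 (Table 6) counts cycles by calendar day from the first dose in this study and leaves the last one open-ended: "Cycle 24 | Day 645 on later".

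Disposition in SAP 9.1.1 has one row for completion: "The number (%) of subjects who completed MT-1186-A03 (% calculated from the number of enrolled subjects in MT-1186-A03". A separate row gives discontinuations by reason. Neither document defines completion or says which row takes a subject whose treatment ended at commercial availability.

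**The concern.** A subject whose country gets the product at, say, Week 40 has reached an end of treatment that the protocol foresees. If that subject is a completer, an adverse event in the follow-up just after Week 40 goes to a block that begins at Day 505. An event after a short exposure then looks like a late-onset event, and it is missing from the block where it arose.

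The primary objective is long-term safety, and this table shows TEAE incidence by treatment period. Under the default in SAP 7.1, percentages use the whole analysis population, so nothing in the table itself would show that a subject counted in Cycle 19-24 never reached Cycle 19.

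The same undefined word affects disposition. A 40-week and a 96-week completer would share one row, and the completion percentage would not tell the reader how many subjects had 96 weeks. Availability is set by country and disposition is also reported by region (SAP 9.4), so the ambiguity carries into that comparison.

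**Working it through.** **Step 1. Reproduce Table 6.** Cycles are 28 days long and Day 1 is the first dose in this study. Cycle c starts on day 28(c − 1) + 1.
- Cycle 19: 28 × 18 + 1 = 505.
- Cycle 24: 28 × 23 + 1 = 645.

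Both match Table 6. The cycle of day d is floor((d − 1)/28) + 1, capped at 24.

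**Step 2. The 96-week completer.** The day of Week w is 7w + 1.
- Week 94: 7 × 94 + 1 = 659.
- Week 96: 7 × 96 + 1 = 673, or Days 666 to 680 with the ± 7-day visit window.

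All are at or after Day 645, so Table 6 already gives Cycle 24. The sentence in 9.3.1 is redundant for these subjects.

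**Step 3. The early ender, if classed as completed.** Let the last treatment cycle end on day 7w. The documents do not state how long follow-up lasts after an early end. As an assumption, onsets 1, 14 and 21 days later were tried, and all three gave the same block. The onset days below run from 7w + 1 to 7w + 21.

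| Treatment ends | Last cycle day | Follow-up onset days | Cycle by onset | Block by onset | Block under 9.3.1 | Blocks too late |
|---|---|---|---|---|---|---|
| Week 20 | 140 | 141-161 | 6 | 1-6 | 19-24 | 3 |
| Week 24 | 168 | 169-189 | 7 | 7-12 | 19-24 | 2 |
| Week 40 | 280 | 281-301 | 11 | 7-12 | 19-24 | 2 |
| Week 60 | 420 | 421-441 | 16 | 13-18 | 19-24 | 1 |
| Week 68 | 476 | 477-497 | 18 | 13-18 | 19-24 | 1 |
| Week 72 | 504 | 505-525 | 19 | 19-24 | 19-24 | 0 |

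In 4-week steps from Week 4 to Week 96, the rule differs from the onset day by three blocks for ends at Weeks 4-20, two at Weeks 24-44, one at Weeks 48-68 and none from Week 72.

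**Step 4. Is the early ender a completer?** These places point to completion:
- The objective and Protocol 10.1.2 build availability into the planned duration.
- The withdrawal criteria in Protocol 9.6 do not list it.
- SAP 5.2 times the final analysis at Week 96 or availability.
- Protocol 10.1.3 contrasts completing the treatment period with terminating early.

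The Protocol synopsis (Methodology) and SAP 4.1 point the other way: both prescribe procedures for subjects who discontinue before Week 96, which could be read to cover any exit before then. Completion is the more natural reading, but it is not stated.

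**Step 5. Number affected.** This would be the early enders classed as completed who have a follow-up TEAE with onset before Day 505. The documents supply none of these inputs. With approximately 140 subjects planned, the count could be anything from zero upward.

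**The case against.** The strongest reply is that the sentence was written only for the Week 94 to 96 follow-up. Protocol 10.1.3 gives Week 96 as its example of the follow-up visit, and SAP 10.2 describes treatment as 24 cycles over 96 weeks. On that reading the rule repeats Table 6 and misplaces nothing. If early enders are classed as discontinued, the rule does not reach them either, and Table 6 places their events by date. Both readings are possible, so the misplacement is conditional. The text still does not choose between them, and two programmers could build different tables.

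Three stronger inferences are tempting and are not supported.
- A reader might conclude that short-exposure events *are* being counted as late. That needs an early ender classed as completed and a follow-up event starting before Day 505; the documents establish neither. For the same reason, a concentration of errors in early-launch countries is conjecture.
- A reader might take this to be the plan's only view of TEAEs by time. SAP 8.4.3.1 also derives and presents time to AE occurrence in days, SAP 9.1.6 gives exposure by cycle, and TEAE listings are provided.
- A reader might infer that survival follow-up stops at launch. Protocol 13.2 already requires phone calls after study-drug discontinuation and does not limit the reason.

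One point against the remedy also has force. If treatment ends at Week 24, the onset-day rule places a follow-up event in Cycle 7, in which that subject took no dose. Table 6 is a calendar definition and SAP 8.6 accepts differences from dosing cycles, so this is consistent with the plan. A separate post-treatment category would avoid it.

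**Conclusion.** The point holds in conditional form. SAP 9.3.1 assigns completers' follow-up TEAEs to the last block without regard to exposure, commercial availability is a planned end of treatment, and completion is undefined. If early enders are classed as completed, their follow-up TEAEs with onset before Day 505 may appear one to three blocks too late. From an end at about Week 72 onward there is no effect, and for 96-week completers the rule is redundant.

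The consequence is limited to the TEAEs-by-Cycle table; the overall, serious, related and fatal TEAE tables do not change. The number of events is unknown and may be zero. The block shifts rest on the assumed follow-up of 1 to 21 days and on treatment ending at a cycle boundary. A change is still justified, because a stated rule gives the wrong block under the more natural reading and the edit is minor. The single completion row is not an error in itself, but without a definition it cannot show how many subjects had 96 weeks.

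**What to change.** In SAP 9.3.1, delete the sentence on follow-up TEAEs of completers and assign every TEAE, including follow-up events, to the cycle of its onset day under Table 6. Alternatively, show post-treatment events of early enders in a separate category.

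In SAP 9.1.1, define completion and replace the single row by two: completed Week 96, and treatment ended at commercial availability. Report both overall and by region.

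The cost is one sentence removed, one definition added and one row split, using dates already collected. No 96-week completer changes block. If early enders would otherwise have been counted as completers, the reported percentage completing 96 weeks will be lower than the pooled figure.
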